4.5.5 Additional safety assessments

4.5.5.1 Clinical laboratory evaluations

A listing in SS will be provided for the woman of childbearing potential showing the urine pregnancy test results as recorded during the study.

No other laboratory examinations are scheduled as per protocol. However, if in case of SAEs relevant laboratory procedures are recorded in the eCRF then these will be listed accordingly.

4.5.5.2 Vital signs

Vital signs (body temperature, pulse rate, systolic and blood pressure) as recorded during screening will be summarized as continuous variables and listed in SS.

Summaries of systolic/diastolic blood pressure will be based on the average of 3 readings as captured in the study eCRF by the PI.

All assessment values as performed at Day 1 and at unscheduled visits (if such visits occur) will be listed in SS.

4.5.5.3 Physical examination

Results of clinically significant physical examination abnormalities following the first self-injection with ZLP-AI are reported as adverse events.

For assessment of tolerability at injection site (as part of physical examination and as defined in the study protocol) see Section 4.5.3.

Physical examination detailed participants' records during screening and in any other study visit will be listed in SS.

4.5.5.4 Columbia-Suicide Severity Rating Scale (C-SSRS)

C-SSRS instrument recorded at screening visit (Visit 1/Day 1) references the lifetime period and the past six months period (Screening/Baseline version) for participants coming from commercial ZLP treatment.

DV0013 participants that entered the study from MG0011 and were previously enrolled in MG0009 are also assessed using the "Screening/Baseline" version of the C-SSRS.

[figure not shown]
DV0013 participants that entered the study from MG0011 and were previously enrolled in MG0010 are assessed using the "Since Last Visit" version of the C-SSRS.

For all participant at all other visits, the C-SSRS version to be considered is the “Since Last Visit” version. Baseline to the last visit (Visit 8/Early Withdrawal) summaries, reference the Intervention Period for all participants.

[figure not shown]
Results of the C-SSRS, as well as the treatment emergent item at the last visit will be summarized in SS by scheduled timepoint using the number of participants and percentage with:

- suicidal ideation,
- suicidal behavior,
- suicidal ideation or behavior,
- self-injurious behavior without suicidal intent.

Suicidal ideation is defined as an event in any of the following 5 categories:

Suicidal behavior is defined as an event in any of the following 5 categories:

Suicidal behavior or ideation is defined as an event in any of the above 10 categories.

Self-injurious behavior without suicidal intent is corresponding to the response to [REDACTED] in questionnaire.

The treatment emergent item at the last visit is defined as any item that is present at Visit 8 / Early Withdrawal Visit that was not present at Day 1 visit.

A by- participant listing of the C-SSRS questionnaire data in SS will be provided.

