#### **8.2.3 Suicidal risk monitoring**

Study participants being treated with ZLP should be monitored appropriately and observed closely for suicidal ideation and behavior or any other unusual changes in behavior. Families and caregivers of study participants being treated with ZLP should be instructed to monitor

participants for the emergence of unusual changes in behavior, as well as the emergence of suicidal ideation and behavior, and to report such symptoms immediately to the Investigator.

Suicidality will be assessed by trained study personnel using the Columbia-Suicide Severity Rating Scale (C-SSRS) (Posner et al, 2011; Mundt et al, 2010). The “Screening/Baseline” version of the C-SSRS will be completed during the Screening Visit for participants coming from commercial ZLP treatment, and the “Since Last Visit” version will be completed at all other time points. The “Since Last Visit” version will be completed at all time points for participants coming from MG0011 as detailed in the SoA (Section 1.3).

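### The C-SSRS treatment-emergent row subtracts Day 1 answers whose recall period depends on entry route, so the same history and on-study item can be flagged differently.

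*SAP*

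**What the plan says.** SAP 4.5.5.4 assigns the Day 1 form by entry route.

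- Commercial supply: the Day 1 instrument "references the lifetime period and the past six months period (Screening/Baseline version) for participants coming from commercial ZLP treatment".
- MG0009, then MG0011: participants "previously enrolled in MG0009 are also assessed using the" Screening/Baseline form.
- MG0010, then MG0011: "DV0013 participants that entered the study from MG0011 and were previously enrolled in MG0010 are assessed using the" Since Last Visit form.

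After Day 1 there is one form: "For all participant at all other visits, the C-SSRS version to be considered is the" Since Last Visit form. The section adds: "Baseline to the last visit (Visit 8/Early Withdrawal) summaries, reference the Intervention Period for all participants". C-SSRS results and the treatment-emergent item are both summarised in the Safety Set by timepoint. The treatment-emergent item is "any item that is present at Visit 8 / Early Withdrawal Visit that was not present at Day 1 visit".

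Protocol 8.2.3 assigns forms differently. There, the Since Last Visit "version will be completed at all time points for participants coming from MG0011", with no exception for those who came through MG0009. Protocol 9.4.2 plans only a by-participant C-SSRS listing.

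**The concern.** A treatment-emergent flag formed by subtraction is interpretable only if what is subtracted means the same thing for everyone. Here it does not. A positive Day 1 answer can refer to any time in life, to the past six months, or to the interval since a previous study visit, depending on how the participant entered.

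The subtraction also fits poorly with the section's own aim. Every participant's Visit 8/Early Withdrawal form is a Since Last Visit form, and the SAP says that these "summaries, reference the Intervention Period for all participants". An item endorsed there is already an on-study report. Removing it because of earlier history answers another question, and answers it with a different look-back on each route.

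The Day 1 row has a related problem. One percentage pools lifetime or six-month positives with since-last-visit positives. That holds even if nobody endorses an item on study.

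At stake is the consistency of a descriptive safety output. No effectiveness endpoint and no sample-size statement depends on it.

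**Working it through.** The documents state no C-SSRS figure, so there is none to reproduce. The check applies the stated rule to every possible history of one item.

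**Inputs**
- Rule (SAP 4.5.5.4): flag = endorsed at Visit 8/Early Withdrawal AND not endorsed at Day 1.
- Day 1 look-back (SAP 4.5.5.4): lifetime and six months for commercial and ex-MG0009 participants; since last visit for ex-MG0010 participants.
- C-SSRS schedule (protocol Table 1-1): Screening, Visit 8 and Early Withdrawal only. The Visit 8 form therefore looks back to Day 1, about 14 − 1 = 13 days.
- Early Withdrawal C-SSRS is mapped to Visit 8 (SAP 4.1.3), so the same rule applies to early withdrawers.

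**Rule applied.** History is written (lifetime, six months, since last pre-study visit), with 1 = item present. The same item is endorsed at Visit 8 in every line.

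| History | Commercial/ex-MG0009, lifetime comparator | Commercial/ex-MG0009, six-month comparator | Ex-MG0010 |
|---|---|---|---|
| (0,0,0) | flagged | flagged | flagged |
| (1,0,0) | not flagged | flagged | flagged |
| (1,1,0) | not flagged | not flagged | flagged |
| (1,1,1) | not flagged | not flagged | not flagged |

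The routes disagree in 2 of 4 profiles with the lifetime comparator and in 1 of 4 with the six-month comparator. The (1,1,0) line assumes that the last MG0011 visit was less than six months before Day 1; the documents do not give that interval.

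**Does another section settle the comparator?** SAP 4.1.2 takes the last non-missing value before the first injection. The lifetime and six-month answers come from the same Day 1 form, so this does not choose between them. The amendment table in SAP 6.14.1 explains why the forms differ by route, but not how the derivation allows for it. The parent-study data listed in SAP 4.1.1.6 do not include C-SSRS.

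**Scale, under assumptions not in the documents.** Take 25 participants, with 20%, 50% or 80% on Screening/Baseline (5, 12 or 20 people), and a probability h of 5% to 20% of a prior positive on the item in the comparator used.
- Expected number with such a history = n × h: from 5 × 0.05 = 0.25 to 20 × 0.20 = 4.0.
- Chance of at least one = 1 − (1 − h)^n: from 1 − 0.95^5 = 23% to 1 − 0.80^20 = 99%.

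These count people with a history, not misclassified events. Misclassification also needs the same item to be endorsed again in the roughly 13 days on study, and nothing in the documents gives a probability for that.

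**One case.** If all 25 have Visit 8 data and one endorses an item, the Visit 8 row shows 1/25 = 4%. The treatment-emergent row shows 4% or 0%, depending on the Day 1 form and the comparator.

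**Effect of the remedies.** Counting every Visit 8/Early Withdrawal endorsement flags all four profiles on every route. Using the six-month answer leaves (1,1,0) split by route.

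**The case against.** The strongest reply is that no information is lost. The plain Visit 8 row uses one form for everyone, includes early withdrawers by mapping, and counts the item whatever was said on Day 1. The by-participant listing shows it too. This stands, and it limits the point to the treatment-emergent row. A reader might infer that on-study events vanish from the report; the documents do not support that.

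A reader might also infer that a commercial participant with any lifetime ideation can never be flagged. That does not follow either. The rule works item by item over five ideation and five behaviour categories, so a different item endorsed at Visit 8 is still flagged. The lifetime answer is also not named as the comparator. Nor is an ex-MG0010 participant with a history always flagged: in profile (1,1,1) no route flags the item.

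Subtracting baseline is a usual way to define emergence, and a single look-back for all routes would give equal flags for equal histories. But a recurrence within that look-back would stay unflagged, and the ex-MG0010 Day 1 form does not collect the longer periods.

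Finally, the public SAP has gaps in this section, and table specifications are in a separate document, so a footnote there might name the recall period. That calls for caution, but the rule as written would still need correcting. The SAP gives an understandable reason for the mixed forms, namely that the MG0009 route had no earlier lifetime assessment. It does not repair the comparison.

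**Conclusion.** The point holds in a limited form. As written, the rule can give different treatment-emergent flags, by entry route, to participants with the same earlier history of an item and the same on-study endorsement. It also leaves the Day 1 comparator open, so two programmers could produce different tables. The difference arises only when the history lies inside the longer look-back and outside the Since Last Visit interval. With no history of the item, all routes agree.

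The number affected cannot be derived, because the route split, the history rates and the MG0011 visit interval are not given. The 0.25 to 4.0 range shows only how many people might carry a relevant history under the stated assumptions.

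Two further points do not depend on any on-study event. The Day 1 percentages mix recall periods. The protocol and SAP also disagree on the form for ex-MG0009 participants; neither that difference nor the addition of C-SSRS summaries to the planned listing is recorded in SAP Table 4-1.

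**What to change.** In SAP 4.5.5.4:

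1. Define an on-study (treatment-emergent) item as any item endorsed on the Visit 8/Early Withdrawal Since Last Visit form, without subtracting Day 1 answers. This matches the section's statement that these summaries refer to the Intervention Period. The row then equals the Visit 8 row, so the two can be merged.
2. Show prior history of the item as a separate descriptor, with its recall period named.
3. Present Day 1 results separately by form version and recall period.
4. Do not substitute the six-month answer as comparator, because the route difference remains.

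Reconcile protocol 8.2.3 with SAP 4.5.5.4 on the form for ex-MG0009 participants. Record that change and the added C-SSRS summaries in SAP Table 4-1.

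The cost is SAP wording, one table shell and entries in Table 4-1. All the data needed are already collected under the plan.

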4.6 Other analyses

4.6.1 Subgroup analyses

The primary estimand as defined in [Table 1–1](#) and expanded in Section [4.2.1](#) and Section [4.2.2](#) will be assessed also by geographical region (North America, Europe) following the same approach in the Safety Set. The same summaries by geographical region will be run for the secondary estimand related to the complete dose delivery.

4.6.2 Self-Injection Training

An individual data listing for all participants in SS will be created providing details on the self-injection training performed at Visit 1 (Screening/Day 1 visit).

4.7 Interim analyses

No interim analysis is planned.

4.8 Changes to protocol-planned analyses

The following changes have been applied in the current SAP vs the study protocol dated 15 December 2023.

Table 4–1: Changes from the DV0013 protocol

Study Protocol	Study SAP update

Definition:
 
Enrolled Set: all participants who have signed an informed consent form.
	
Definition
 
Enrolled Set: all participants who have signed an informed consent and are eligible candidates for the study (screen failures excluded).

Screened Set (ScS) has not been defined in the study protocol
	
ScS has been defined in the SAP as all participants who have signed the informed consent form.

For the primary estimand, as sensitivity analysis, any missing data were to be imputed as administration failure.
	
Sensitivity analysis has been removed because based on the definition of the primary estimand, no missing values are expected.

Population level summary of the secondary estimand regarding the complete dose delivery at Visit 1 and at Visit 8 is based on the proportion of participants:
 
Proportion of participants, along with the 95% CI.
	
Population level summary of the secondary estimand regarding the complete dose delivery at Visit 1 and at Visit 8 is based on the proportion of used ZLP-AIs and returned (for Visit 8). Therefore, the population level summary of the estimand has been phrased as:
 
Complete dose delivery: completeness of the delivery as confirmed by the Investigator at Visit 1 and at Visit 8. The entire dose of IMP should be completely delivered (ie, the yellow plunger that can be seen through the device window should be completely depressed)

Table 4–1: Changes from the DV0013 protocol

Study Protocol	Study SAP update
Population level summary of the secondary estimand regarding the complete dose delivery at Visit 1 and at Visit 8 by region was not defined.	Population level summary of the secondary estimand regarding the complete dose delivery at Visit 1 and at Visit 8 will be also displayed by region.

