Participants will receive the doses of IMP listed in Table 6-1 based on their weight and their established dosing regimen in MG0011/commercial supply.

Regardless of the assigned dose regimen, participants will perform a single self-administration with the ZLP-AI, as specified in the SoA (Section 1.3) on Days 1 to 14.

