#### 9.3.1 Primary estimand/primary endpoint analyses

The primary outcome variable is defined in [Table 3-1](#).

The proportion of effective self-administrations will be tabulated for the ZLP-AI combination product using the SS population. The 95% CIs based on the Exact Binomial method will be reported. As a sensitivity analysis, the primary endpoint will also be evaluated, where any missing self-administration will be considered as an administration failure. In addition, the proportion of effective self-administrations may be described by geographical region as well.

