## **9.8 Determination of sample size**

This study will not be powered with respect to any endpoint, and sample size is based on practical considerations. The number of participants and their diagnosed conditions are summarized below.

Given the rare diseases framework of the gMG indication and the fact that the device is not life supportive, the sample size is based on previous experience and the operating functions of the ZLP-AI.

Participants from MG0011 or those who are currently being treated with commercial ZLP and are on a stable dosing regimen for at least 1 month will be screened at approximately 20 sites in the US and Europe in order to enroll at least 25 participants who use the ZLP-AI at Visit 1 and to obtain approximately 350 self-administrations.

Public Copy  
This document cannot be used to support any marketing authorization application and any extensions or variations thereof.

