1.2 Study design

DV0013 is a Phase 3b, multicenter, single arm, open-label study to evaluate the safe and effective use of a ZLP-AI combination product for sc self-administration of ZLP solution (the IMP) by study participants with generalized myasthenia gravis (gMG), planned to be conducted within Europe and United States in 13 centers.

The study will aim to reflect real-world use scenarios by including participants who are already self-administering ZLP using the PFS on a once-daily dosing regimen as part of the MG0011 long-term open-label extension (OLE) study or who are on commercial ZLP treatment for at least 1 month prior to Screening.

DV0013 consists of 9 visits (2 clinic visits and 7 remote telephone visits) and 14 self-administrations using the ZLP-AI, during which no dose modification is allowed. Participants should continue on the same weight-based dose that they were self-administering in MG0011 or commercial ZLP dose they were on prior to enrolling in DV0013.

Intervention Period (Treatment Period)

- Visit 1 (Screening/Day 1): Each study participant will be provided with training by study personnel in self-administration using the ZLP-AI and will receive the written instructions for use (IFU). Following the training, the study participant will perform self-administration at the clinic using the ZLP-AI.
- Visit 2 to Visit 7: No additional training will be performed; however, the IFU will be available. The study participant will perform self-administration at home using the ZLP-AI. These visits will be remote visits using a telephone call. During the call, the Investigator will ask about the self-administration and document any adverse events and adverse device effects

(AEs and ADEs), any changes in concomitant medication use, and/or medication errors occurring in the course of the self-administration. Telephone visits which would be scheduled to occur on a weekend day or national holidays may be skipped, and the data for the respective days (Saturday and Sunday or national holiday) will be collected on the next clinic business day (eg Monday).

- Visit 8: The study participant will perform self-administration at the clinic using the ZLP-AI. The Investigator will collect all used devices from participants and will check completeness of the delivery for the collected devices. All used devices will be returned to UCB for a separate assessment of structural and mechanical integrity.

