4.1.1.5 Analysis periods

Based on the specific requirements of the analyses, the concept of the definition of periods need to be considered for the study, is defined in detail below.

The total duration of study participation for all participants will be up to approximately 21 days, including single Screening/Day 1 Visit, a 14-days Intervention Period and a safety follow up period of up to 7 days (± 3). The end of the study is defined as the date of the last visit of the last participant in the study.

Screening Period: starts at the day of ICF signature (any time prior to the first dosing with ZLP-AI on site) and ends at the date/time of first application of ZLP-AI on site.

Intervention Period (Treatment Period): starts at the date/time of the first application of ZLP-AI on site. The end of intervention period is the date of the last ZLP-AI application on site or the date of Early Withdrawal Visit was performed, as applicable.

All participants in the Safety Set will be considered to have entered the Intervention Period. A participant is considered to have completed the Intervention Period if the Visit 8 visit on site at day 14 has been performed.

If a participant does not have the last planned visit or Early Withdrawal visit, then either the date of the last scheduled (on site or phone call visits) or unscheduled visit during the considered period or the date of the last known dose of study drug during the considered period, whichever is later, will define the end date of the Intervention Period.

Safety Follow-Up Period: one day after the end of the Intervention Period ending after the final assessments on the Safety Follow-up visit. Participants with assessment after the Intervention Period are considered to have started the Follow-up Period.

The end of study for each participant is defined as the last visit attended (as planned, Early Withdrawal, phone visit) in the Intervention Period or in the safety follow up period. If a participant does not have the last planned visit or Early Withdrawal visit, then either the date of the last scheduled (on site or phone call visits) or unscheduled visit during the considered period or the date of the last self-injection with ZLP-AI intake during the considered period, whichever is later, will define the end date of the Intervention Period.

A participant is considered to have completed the study if he/she has completed all periods of the study, including the Intervention Period and SFU phone call.

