4.2.3 Sensitivity analysis

As a sensitivity analysis on the primary estimand the following will be considered in the Safety Set.

$$p = [\text{Number of all ZLP-AIs with complete dose delivery}] / \text{Number of all ZLP-AIs that should have been used in the Intervention Period.}$$

The number of ZLP-AIs that should have been used in the Intervention Period for each participant will be calculated as follows: [Date of last ZLP-AIs self-administration – Date of first ZLP-AIs self-administration + 1].

The 95% CI of the proportion based on the Exact Binomial method will be reported as well.

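### The SAP both removes and specifies the sensitivity analysis of the primary estimand, and the version it specifies leaves out planned injections not given after early stopping

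*SAP*

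**What the plan says.** Protocol 9.3.1 adds a sensitivity analysis in which "the primary endpoint will also be evaluated, where any missing self-administration will be considered as an administration failure". Protocol 9.3 and 9.6 repeat the rule for missing data on the primary estimand.

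On the planned number of injections, Protocol 6.1 states that "participants will perform a single self-administration with the ZLP-AI, as specified in the SoA (Section 1.3) on Days 1 to 14", and SAP 1.2 gives the same total: "DV0013 consists of 9 visits (2 clinic visits and 7 remote telephone visits) and 14 self-administrations using the ZLP-AI".

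The SAP then says two different things.

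- Section 4.8, Table 4-1, which lists departures from the protocol: "Sensitivity analysis has been removed because based on the definition of the primary estimand, no missing values are expected".
- Section 4.2.3 sets out a sensitivity analysis on the primary estimand in the Safety Set, with an exact binomial 95% CI. The numerator is devices with complete delivery and the denominator is devices that should have been used. On that denominator: "The number of ZLP-AIs that should have been used in the Intervention Period for each participant will be calculated as follows". The formula that follows is the last self-administration date minus the first, plus 1.

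The main analysis in SAP 4.2.2 divides by devices used and returned. SAP 4.1.1.2 imputes no endpoint data, and SAP 4.2.4 plans no supplementary analysis.

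**The concern.** There are two separate problems.

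First, a programmer cannot tell from the SAP whether the sensitivity table is to be produced. Table 4-1 describes the current SAP against the protocol, so it is not superseded text. The amendment log in SAP 6.14 mentions neither a removal nor a reinstatement.

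Second, if 4.2.3 is followed, its expected count ends at the participant's own last injection. Someone who stops early shortens their own denominator. SAP 4.2.2 expects no missing data because its denominator holds only devices that came back used, so a missing-data check has to look outside that set. Section 4.2.3 does so for gaps in the middle of treatment but not for the tail. SAP 4.1.3 foresees stopping before Visit 8. Protocol 7.2 names injection site reactions and personal preference among the reasons for withdrawal, and either could be connected with the device. What is at stake is whether the one analysis labelled as a sensitivity analysis of the primary endpoint can show the effect of such stops.

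**Working it through.** **Inputs**

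- Participants: 25, the minimum in Protocol 9.8 ("enroll at least 25 participants who use the ZLP-AI at Visit 1 and to obtain approximately 350 self-administrations").
- Planned injections: 14 each, one a day on Days 1 to 14 (Protocol 6.1, SAP 1.2).
- Interval: two-sided 95% exact binomial (SAP 4.2.2 and 4.2.3).
- Number and timing of early stoppers: assumed, because neither document gives a dropout rate.

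**The plan's own figure.** 25 × 14 = 350, which reproduces the target of about 350 self-administrations.

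**Set-up.** Let k participants stop after Day d. Everyone else uses all 14 devices, and every used device is complete and returned. Devices used: U = (25 − k) × 14 + k × d.

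- SAP 4.2.2: U/U.
- SAP 4.2.3: a stopper's expected count is d − 1 + 1 = d, so the result is again U/U.
- 14 planned each: U/350.

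For k = 2 and d = 3: U = 23 × 14 + 2 × 3 = 328. The 2 × 11 = 22 injections not given appear in neither the numerator nor the denominator of 4.2.3.

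| Early stoppers (assumed) | SAP 4.2.2 and 4.2.3 | 14 planned each |
|---|---|---|
| none | 350/350 = 100% (99.0-100) | 350/350 = 100% (99.0-100) |
| 1 after Day 7 | 343/343 = 100% (98.9-100) | 343/350 = 98.0% (95.9-99.2) |
| 1 after Day 3 | 339/339 = 100% (98.9-100) | 339/350 = 96.9% (94.4-98.4) |
| 2 after Day 3 | 328/328 = 100% (98.9-100) | 328/350 = 93.7% (90.6-96.0) |
| 3 after Day 1 | 311/311 = 100% (98.8-100) | 311/350 = 88.9% (85.1-92.0) |

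**If the last device also fails.** With 2 stopping after Day 3 and the last device of each incomplete, 4.2.3 gives 326/328 = 99.4% (97.8-99.9). With 14 planned each the result is 326/350 = 93.1% (90.0-95.6).

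**What 4.2.3 does catch.** With no early stoppers and 3 devices skipped or unreturned between first and last use, 4.2.2 gives 347/347 = 100% (98.9-100) and 4.2.3 gives 347/350 = 99.1% (97.5-99.8).

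The exact intervals treat injections as independent. In the stopping examples the failures come in blocks from one to three people, so the shift in the proportion is informative but the interval width is not.

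**The case against.** The contradiction between Table 4-1 and 4.2.3 has no good answer. Against the denominator point, several things can fairly be said.

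- **The protocol does not fix 14 as the denominator.** A reader might infer that Protocol 9.3.1 plainly requires it. It does not say outright that injections after withdrawal are missing; the term could mean a skipped dose or a lost device. This stands. The reading used here rests on 14 being planned for each participant and on the wording that "any missing self-administration will be considered as an administration failure".
- **The SAP's Intervention Period does not settle it.** A reader might infer that 4.2.3 breaks SAP 4.1.1.5. That section says: "The end of intervention period is the date of the last ZLP-AI application on site or the date of Early Withdrawal Visit". For completers this is the last injection, so the two sections agree. For withdrawers they can differ by the days up to the Early Withdrawal visit, but 4.1.1.5 does not give 14 either.
- **Section 4.2.3 is not empty, and early stopping is reported elsewhere.** It counts gaps within the span. Disposition (SAP 6.2), events leading to withdrawal (4.5.2.3), device accountability (4.2.2) and compliance (6.10) show stops indirectly. None of these puts the stops into the primary proportion. The compliance percentage also ends at the Early Withdrawal visit where there is one: a last dose on Day 3 with that visit on Day 6 gives 3/6 = 50%, not 3/14 = 21.4%.
- **Stopping may have nothing to do with the device.** Protocol 7.1 and 7.2 include illness, pregnancy and administrative reasons. This stands, and it is why the 14-planned figure is a worst case. The documents do not support the inference that stops are mostly device failures.
- **The study is descriptive.** It has no hypothesis test, power target or stated success threshold, so no pass or fail decision turns on this figure.

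**Conclusion.** Both parts hold, with different weight.

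The SAP contradicts itself on whether a sensitivity analysis of the primary estimand is done. That needs correction whatever the dropout turns out to be.

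The first-to-last count in 4.2.3 cannot reflect planned injections lost after early stopping, and for those losses it adds nothing to the main analysis. This is a should-fix. Its size depends wholly on the assumed stopping pattern: zero with no early stoppers, 2.0 percentage points for one stop after Day 7 (100 − 98.0), and 6.3 for two stops after Day 3 (100 − 93.7), if all used devices are complete and returned. It also rests on reading the protocol's rule as covering all 14 planned injections, which the protocol implies but does not state.

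A reader might infer that the primary result is overstated. The documents do not support that: the primary estimand concerns self-administrations that took place, and its estimate is unaffected.

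**What to change.** 1. In SAP 4.2.3, set the denominator to 14 planned self-administrations for each Safety Set participant, and count every one without confirmed complete delivery as a failure. Label the result a worst case that also counts stops unrelated to the device. The existing first-to-last version may be kept beside it, since it isolates gaps during use.
2. State in the same section that injections not given after early stopping count as missing for this analysis, so that the reading of Protocol 9.3.1 is explicit.
3. Rewrite the Table 4-1 row to describe the analysis actually planned and how it differs, if at all, from the protocol's.

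The cost is SAP wording and one programmed denominator. All the data are already collected. The drawback is a sensitivity figure that may be less favourable and that scores withdrawals for any reason as failures; the label and the disposition table let a reader judge that.
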